Currently, there is no clinical evidence that supports the routine administration of 100% oxygen prior to intubation is essential or beneficial. In the contrary, it also remains undetermined if lower fractions of inspiratory oxygen during the induction period of anesthesia may attenuate lung injury or other cellular damage derived from the oxygen toxicity. Therefore, the findings of this proposed clinical study may provide fundamental evidence for the use of different oxygen concentrations in clinical anesthesia during the induction period, and determine the effects of inspiratory oxygen concentrations on the general postoperative outcomes after general anesthesia.

IV. Purpose of the study

The aim of this study is to determine the effect of preoxygenation with pure oxygen ($\text{FiO}_2=1$) or lower partial pressure of oxygen ($\text{FiO}_2=0.6$) on the development of hypoxemia during anesthesia and major complications at 3 days after surgery. These measurements include hemodynamic parameters, acute lung injury, wound healing, pain, other systemic complications, all cause mortality, and hospital length of stay.

V. Study design: this is a randomized, open-label, observer-blind and non-inferiority clinical trial.

1. Research model: Two-group parallel interventional study.
2. Control group: Preoxygenation with 100% oxygen during the induction phase of anesthesia
3. Blind method: Open-label, observer-blind.
4. Randomization: Block randomization using randomization generator software.

VI. The number of subjects:

This study anticipates in enrolling 500 participants in each month and it will take three months to enroll a total of approximate 1500 participants.

VII. Inclusion criteria:

1. A patient who is scheduled for an elective surgery and required for anesthesia with endotracheal intubation.
2. Age of the patient is between 18 and 65 years old.
3. Patient's American Society of Anesthesiologists (ASA) Physical Status is I-III.

VIII. Exclusion criteria.

Patients who:

1. Have difficult airway for ventilation or intubation.
2. Have severe lung disease (including any acute respiratory infection).
3. Were diagnosed of coronary artery disease or myocardial infarction.
4. Have severe heart failure (NYHA Fc \geq III).
5. Have liver cirrhosis (Child-Pugh's score \geq B).

6. Have acute or chronic kidney disease (Creatinine ≥ 2 mg/dl).
7. Have severe anemia (hemoglobin ≤ 8 mg /dl).
8. Have a body mass index ≥ 35 .
9. Are currently pregnant.

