10. Have not enough fasting time, intestinal obstruction or severe gastroesophageal reflux.
11. Received emergency surgery, cardiac surgery, craniotomy, or pulmonary surgery.
12. Have mental incapacitation, confusion, dementia, mental retardation, or are unable to complete the consent independently.
13. Refuse to participate in this study.

IX. Research processes:

This research study is a randomized, open-label and observer-blind trial. Patients who meet the eligibility criteria (without any exclusion criteria) and agree to join the study are randomly assigned to either high oxygen (FiO₂=1) or lower oxygen (FiO₂=0.6) group. A research assistant, who is not involved directly in patient care, will randomly assign the patients to the high oxygen (FiO₂=1) or lower oxygen (FiO₂=0.6) group.

After entering the operating room on the day of surgery, a pulse oximeter will be applied to the patient to determine the baseline levels SpO₂. Preoxygenation with different percentages of inspiratory oxygen will be administered via a face mask for 8-10 minutes before intubation of an endotracheal tube. Pulse oximeter and other standard hemodynamic parameters will be continuously monitored throughout the entire induction period. After the endotracheal tube is successfully established, the patient will be processed for maintenance of anesthesia and surgical procedure

according to the clinical practice.

X. Assessment Indicators (objective measures based on research objectives)

1. The primary endpoint of this study is the development of hypoxemia (defined as SpO₂< 92%) during the induction of anesthesia.
2. The composite secondary endpoint is the development of complications within three days after surgery, which include acute lung injury, lung collapse, pneumonia, wound infection, delayed wound healing, severe postoperative pain, prolonged hospital stay and mortality.

XI. Withdrawal from the study (Please provide a brief description of the assessment criteria and conditions for withdrawal from the study)

1. Patient or his/her family voluntarily withdraws from the study.
2. A baseline level of SpO₂ < 92% measured at operating room.

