3. A Data & Security Monitoring Board (DSMB) will be established to monitor the progress of the study. This monitoring board consists of a clinical expert, a biometric expert and a human rights expert. The adverse events, number of patients who dropped out of the trial, compliance with the test, the integrity, timeliness, and the quality of the data will be closely monitored by the board members.

XII. Consent form acquisition process

The physician anesthesiologists will illustrate the purpose of study, research procedures, potential risks and follow-up of the study during the preanesthesia visit. The informed consent will then be obtained from the patient.

XIII. The expected risks, side effects and treatment

Expected risks and side effects: the administration of lower oxygen concentration (FiO₂= 0.6) during preoxygenation period may cause hypoxemia. Since tissue oxygenation will be continuously monitored throughout the anesthesia period, the development of hypoxemia during this period will be detected by the anesthesia team. Hypoxemia will be treated by the in-charge anesthesiologist according to the standard clinical guidelines, including increased concentrations of inspiratory oxygen, application of positive pressure ventilation, and increased minute ventilation.

XIV. Data Collection and Management

1. Data collection:

Medical records Questionnaire Interview Photography or photography
 Others _____

2. Person who may contact with the participants' information:

Principal Investigator Co-principal Investigator Research Assistant
 Program auditing staff Others _____

3. Data processing

Encoding identification Encryption De-linking Others _____

4. Data preservation:

The time for keeping the data: Destruction after the end of the project

Continue to save and reuse after the end of the project.
 Location of keeping the data: in the Department of Anesthesiologist Office in E-da Hospital.

■ The data in-charge person: [name], [name] (Vice-superintendent in E-da Cancer Hospital)

XV. Sample collection and samples derivative management

■ Does collect any specimen? NO.

XVI. Statistical analysis

All quantitative variables will be using a two-way RM ANOVA or unpaired t-test. And all qualitative variables will be using χ^2 test followed by the posthoc 2×2 Fisher exact test.

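### Section XVI names a two-way RM ANOVA with no sphericity correction and no way to use partial records; uncorrected on serially correlated induction readings, its arm-by-time test would exceed a nominal 5%

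*Combined protocol and SAP*

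**What the plan says.** Section XVI, Statistical analysis, covers all quantitative data in one sentence: "All quantitative variables will be using a two-way RM ANOVA or unpaired t-test". It does not say which variables go to which test, at which times, with what covariance assumption or significance level, or what happens when a reading is missing. A second sentence assigns qualitative variables to chi-square and Fisher tests.

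Other sections show what could be measured repeatedly. Section IX says that pulse oximetry and "other standard hemodynamic parameters will be continuously monitored throughout the entire induction period", and that preoxygenation "will be administered via a face mask for 8-10 minutes before intubation of an endotracheal tube". Section IV describes the study's measurements: "These measurements include hemodynamic parameters, acute lung injury, wound healing, pain", followed by further outcomes. Section X makes the primary endpoint the occurrence of hypoxemia during induction, and the secondary endpoint a composite of complications within three days.

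**The concern.** A repeated-measures ANOVA is relevant only to something measured more than once per patient. SpO2 and hemodynamics during induction are the only quantities that the documents describe as followed over time, so they are the natural candidates.

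Readings taken minutes apart are usually more alike the closer they are in time. The classical RM ANOVA assumes sphericity (equal variances of all pairwise differences between times), and that pattern violates it. The F test for arm by time, which asks whether the two oxygen groups follow different courses, then rejects too often. A large sample does not help, because the excess depends on the shape of the covariance matrix and not on the number of patients.

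The classical method also needs a complete row for each patient, so one absent reading removes that patient from the whole analysis. At stake is the reliability of supportive statements about the SpO2 and hemodynamic course.

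**Working it through.** **The plan's own figure.** Section VI gives "This study anticipates in enrolling 500 participants in each month" and "it will take three months to enroll a total of approximate 1500 participants". 500 × 3 = 1500, so the accrual arithmetic agrees. There is no power calculation to reproduce.

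**Inputs from the documents.** Two arms (section V: "Two-group parallel interventional study"); about 1500 patients; RM ANOVA (section XVI).

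**Inputs assumed because the documents do not give them.** 1:1 allocation (section V says only "Block randomization using randomization generator software"), hence 1500 / 2 = 750 per arm; nominal level 5%; k equally spaced readings; AR(1) correlation with lag-1 value ρ from 0.5 to 0.95; equal variances unless noted; no true arm difference; no correction applied.

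**Step 1: departure from sphericity.** Let λ be the k−1 non-zero eigenvalues of the centred covariance matrix. Box's epsilon is ε = (Σλ)² / [(k−1) Σλ²], and ε = 1 means sphericity holds. For k = 3 and ρ = 0.5, the total is Σλ = 3 − 5.5/3 = 1.1667. One eigenvalue is 1 − 0.25 = 0.75, so the other is 0.4167. Then ε = 1.3611 / [2 × (0.5625 + 0.1736)] = 0.925.

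**Step 2: true rejection rate.** With 2n − 2 = 1498 between-patient degrees of freedom, the uncorrected arm-by-time statistic under the null is distributed as [Σλχ²(1)/(k−1)] / [Σλχ²(1498)/(1498(k−1))]. It is compared with the 5% point of F with k−1 and 1498(k−1) degrees of freedom. Results from 200,000 draws per case:

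| Readings k | ε at ρ = 0.5 / 0.8 / 0.95 | Null rejection at ρ = 0.5 / 0.8 / 0.95 |
|---|---|---|
| 2 | 1 / 1 / 1 | 4.9 / 5.0 / 4.9% |
| 3 | 0.925 / 0.849 / 0.812 | 5.4 / 5.7 / 5.9% |
| 5 | 0.809 / 0.631 / 0.551 | 6.2 / 7.4 / 8.2% |
| 10 | 0.692 / 0.411 / 0.298 | 7.5 / 10.5 / 12.3% |

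Direct simulation of patient data (4,000 trials per case) agrees: 7.2% for k = 5, ρ = 0.8; 11.4% for k = 10, ρ = 0.8; 11.6% for k = 10, ρ = 0.9.

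**Step 3: sensitivity to the covariance pattern.** Under compound symmetry with k = 5 the rate is 5.0%. If variances are larger at the last readings, it is 8.2–11.6% with k = 5 and 9.1–15.5% with k = 10. With k = 20, equal variances and ρ = 0.95 it is 16.5%.

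**Step 4: effect of a correction.** Multiplying both degrees of freedom by the true ε (for example 4 × 0.551 = 2.2 for the numerator at k = 5, ρ = 0.95) brings the rate to 4.8–5.2% in every case run.

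**Step 5: what is not affected.** The arm main effect compares each patient's average and does not need sphericity. Simulated at ρ = 0.9 (200 per arm, 4,000 runs), it rejects in 5.0% of null cases with 5 readings and 4.4% with 10. The simulation error is about √(0.05 × 0.95 / 4000) = 0.3 percentage points.

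**Step 6: partial records.** If a share m of readings is missing independently at each time, a complete-record analysis loses 1500 × [1 − (1 − m)^k] patients. For m = 1%, 2% and 5% this is 74, 144 and 339 with k = 5, and 143, 274 and 602 with k = 10. These values of m only show how fast losses add up; they are not estimates for this trial.

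**The case against.** The strongest reply is that the plan never says closely spaced induction readings go into the RM ANOVA. Monitoring a signal continuously is not a schedule of analysed values. Three event-based readings (baseline, end of preoxygenation, after intubation) fit the text equally well, and then the rate is below 6%. Nor does section XVI exclude an epsilon adjustment; its absence is an omission, not a stated choice. All of this stands, and it is why the size is given only conditionally.

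Four stronger readings are tempting, and the documents do not support them:

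- *The plan's test has an error rate of 8–12%.* That needs roughly 6–10 readings with correlation 0.8–0.95. Neither figure is in the documents.
- *All quantitative arm comparisons are too liberal.* Only the within-patient tests are. The arm main effect and the t-test keep their level.
- *Pain comparisons over days would lose patients at discharge.* Pain is never described as a repeated score. Section X has severe postoperative pain as one component of a composite event, so no dropout rate or loss of precision can be derived.
- *The 8–10 minute window means that patients will be dropped.* Readings up to minute 8, or tied to events, could exist for everyone. Exclusion of incomplete records is a property of the classical method, not a rule in the plan.

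It is also fair to say that a mixed model is not the only remedy for the error rate: the epsilon correction alone repairs it. It does nothing, however, for patients with partial records.

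**Conclusion.** The point holds in conditional form and is minor. The named method lacks a sphericity correction and cannot use partial records, and a better standard method is available at almost no cost. The excess is negligible with 2 or 3 readings and material with about 10, where the rate can be more than double the nominal level. The unstated number and spacing of readings, more than anything else in the plan, decide whether it matters. It rests on the assumed serial correlation, equal spacing, 5% level and absence of a correction. The loss of patients is real in principle but cannot be sized. No named endpoint depends on the RM ANOVA: both are qualitative, so only supportive SpO2 and hemodynamic comparisons are touched.

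**What to change.** In section XVI, name the supportive variables that are measured repeatedly, and fix their analysis time points so that every patient can contribute, for example by tying them to events rather than to elapsed minutes. Replace the RM ANOVA by a linear mixed model fitted by REML, with arm, time and arm-by-time as fixed effects and an unstructured covariance. Use every available reading, and report the arm difference with its 95% interval at each time. An unstructured matrix for 10 times has 10 × 11 / 2 = 55 parameters, which about 1500 patients can support. Keep the unpaired t-test for quantities measured once.

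If the RM ANOVA is retained, state that the Greenhouse-Geisser correction will be applied to the within-patient tests and say how incomplete records are handled.

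The cost is a few sentences in the plan and slightly more analysis work with standard software. No new data are needed. The mixed model does not recover information that was never recorded, and its estimates rely on readings being missing at random.

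### The three-day complication composite is compared without adjustment for age, ASA class, BMI or operation type, which may give up some precision to the extent that these factors predict it

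*Combined protocol and SAP*

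**What the plan says.** Section X, item 2, defines the outcome: "The composite secondary endpoint is the development of complications within three days after surgery". Its components are lung events, wound infection and slow wound healing, severe pain, prolonged stay and death. Whether any of these occurs is a yes/no outcome.

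Section XVI has two sentences. The second, which begins "And all qualitative variables will be using", assigns a chi-square test followed by a 2×2 Fisher exact test. The composite falls under that rule. No covariate, stratified test or adjusted estimate is named.

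Four baseline factors enter the eligibility criteria:
- age, limited to 18 to 65 (section VII, item 2);
- ASA class: "Patient's American Society of Anesthesiologists (ASA) Physical Status is I-III" (section VII, item 3);
- BMI, with 35 or more excluded (section VIII, item 8);
- the operation, which must be elective and need intubation (section VII, item 1), with an exclusion for patients who "Received emergency surgery, cardiac surgery, craniotomy, or pulmonary surgery" (section VIII, item 11).

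Section V describes a "Two-group parallel interventional study" and gives the allocation method as "Block randomization using randomization generator software". No stratification factor is named.

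**The concern.** Eligibility takes in almost any elective operation that needs intubation. Wound problems, severe pain and length of stay can reasonably be expected to differ between operations, and perhaps with ASA class, age and BMI. If they do, part of the spread in the composite is predictable before treatment. A crude comparison leaves that part in the standard error, and an adjusted one takes it out.

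At stake is the width of the confidence interval for the composite, which is the only secondary endpoint listed in section X. A wider interval makes an inconclusive result somewhat more likely. The sample size offers no reassurance that there is precision to spare, because it is justified only by recruitment: "This study anticipates in enrolling 500 participants in each month", and "it will take three months to enroll a total of approximate 1500 participants".

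**Working it through.** **The plan's own figure.** 500 per month × 3 months = 1500, which agrees with section VI. This is recruitment arithmetic. No error rate, power, event rate, effect or margin is given, so no power calculation can be reproduced.

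**Inputs.** Total 1500 is from section VI. The allocation ratio is not stated, so 1:1 (750 per arm) is assumed. The composite rate and the strength of the covariates are not stated, so every risk below is an assumption.

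**Formulas.** Take three operation classes of equal size.
- Crude variance: V = p(1−p), with p the mean of the class risks.
- Adjusted variance: W = mean of the within-class p(1−p).
- Ratio = W/V; variance reduction = 1 − ratio.
- Equivalent extra patients = 1500/ratio − 1500.
- 95% CI half-width = 1.96·√(2v/750), with v equal to V or W.

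**Worked case, 5/20/45%.** p = 70/3 = 23.3%. V = 0.2333 × 0.7667 = 0.1789. W = (0.0475 + 0.1600 + 0.2475)/3 = 0.1517. Ratio = 0.848, so the reduction is 15%. Extra patients = 1500/0.848 − 1500, about 269. Half-width: 1.96·√(2 × 0.1789/750) = 4.28 points crude, and 1.96·√(2 × 0.1517/750) = 3.94 points adjusted.

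| Class risks (%) | Overall (%) | V | W | Ratio | Reduction | Extra patients | Half-width, crude → adjusted (points) |
|---|---|---|---|---|---|---|---|
| 5/20/45 | 23.3 | 0.1789 | 0.1517 | 0.848 | 15% | 269 | 4.28 → 3.94 |
| 10/20/35 | 21.7 | 0.1697 | 0.1592 | 0.938 | 6% | 99 | 4.17 → 4.04 |
| 15/20/25 | 20.0 | 0.1600 | 0.1583 | 0.990 | 1% | 16 | 4.05 → 4.03 |
| 1/3/8 | 4.0 | 0.0384 | 0.0375 | 0.977 | 2.3% | 35 | 1.98 → 1.96 |

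The last row is the rare-composite case. Even an eightfold spread in risk then gains almost nothing.

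**Check with all four covariates.** A simulation of 1500-patient trials (1500 trials per scenario, relative risk 0.75) compared the crude risk difference with the standardised one from a logistic regression on operation class, ASA class, age and BMI. Weak, moderate and strong refer to assumed odds ratios between the extreme operation classes of about 1.8, 4.5 and 16, with the other covariates scaled to match.

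| Control rate | Variance reduction: weak / moderate / strong | Power, moderate: crude → adjusted | Power, strong: crude → adjusted |
|---|---|---|---|
| 5% | 0% / 1% / 4% | 21.9% → 21.9% | 21.5% → 22.4% |
| 10% | 1% / 4% / 8% | 41.0% → 40.9% | 40.2% → 43.5% |
| 20% | 1% / 6% / 17% | 73.8% → 76.0% | 71.3% → 78.5% |
| 30% | 0% / 6% / 21% | 91.1% → 92.9% | 90.6% → 95.3% |

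Adjusted power here is for the test of the arm coefficient in the logistic model. With 1000 trials per scenario under no effect, type I error was 4.3–5.6% crude and 3.8–6.4% adjusted, with no consistent inflation given simulation error.

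**The case against.** The strongest reply is that nothing here is wrong. Under randomisation the crude test is valid, and the gain depends wholly on prognostic strength, about which the documents are silent. Patients are aged 18 to 65, ASA I–III and free of several serious comorbidities, so the composite may be uncommon. Severe pain and prolonged stay are not defined. If prolonged stay is judged against what is usual for the procedure, much of the operation effect disappears. With moderate predictors the gain in power is nil at rates of 5% and 10%, and about 2 points at 20%. All of this stands, and it limits the size of the point.

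The data are also not quite free. Eligibility requires only that certain operations be ruled out and that BMI be below 35. The documents do not show that an operation category or an exact BMI is recorded for analysis. Both are probably in the medical record, but coding operations for about 1500 patients is some work. This stands as a modest cost.

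Three stronger readings are tempting, and the documents do not support them.
- A reader might infer that the operation largely drives the composite. That is plausible from the components, but no rate or statement in the documents shows it.
- A reader might count the removal of chance imbalance in operation mix as a second benefit. It is the same gain: the between-class variance removed (0.1789 − 0.1517 = 0.0272 in the worked case) is what chance imbalance contributes, and the crude standard error already covers it.
- A reader might take the composite to be the only test of postoperative outcome. Section IV also lists lung injury, wound healing, pain, mortality and length of stay, and section XVI covers all variables.

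**Conclusion.** The point holds as a conditional loss of efficiency. The composite is analysed crude, four baseline factors are established before assignment, and prespecified adjustment would tighten the estimate if they are prognostic. The gain runs from almost nothing, with weak covariates or a rare composite, to roughly 15–20% of the variance, with strong covariates and a common composite. In the strongest of the three-class cases the half-width narrows from 4.28 to 3.94 points. These figures rest on 750 per arm, no dropout, and assumed risks and odds ratios.

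It would be wrong to read this as bias, invalid inference or an inflated error rate. The reason to act is that the change costs little, and that the covariates and operation categories have to be fixed in advance if the adjustment is to be credible.

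**What to change.** In section XVI, state that the composite will be analysed by logistic regression on arm, operation category, ASA class, age and BMI, and that the result will be reported as the standardised (marginal) risk difference with its 95% confidence interval. Keep the crude proportions and crude test as description or as a sensitivity analysis.

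Define the operation categories before any outcome data are seen, with a rule for merging sparse ones. State in advance how the covariate list will be shortened if events are few. Make sure that operation category and the BMI value are captured as data.

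The cost is a few sentences in the plan, the defining and coding of operation categories from records, and a little more analysis. No extra patients or procedures are needed.
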